Primary Objective To assess long-term tolerability and safety of sargramostim in individuals with mild-to-moderate Alzheimer's Disease (AD).	Effects of sargramostim on white blood cell mobilization will be determined by CBCs with differential. Comprehensive metabolic panels (CMPs), electrocardiograms (ECGs), serology testing for antidrug antibodies (ADAs), physical exams, and high-resolution MRI scans to identify amyloid-related imaging abnormalities (ARIAs) will be performed, and vital signs and adverse events (AEs) will be
	monitored.
Secondary Objective:	Secondary Endpoint Change in cognition from Baseline to End of Treatment (EOT) visit as
To test the hypothesis that sargramostim treatment, as compared to placebo, slows or halts cognitive decline, or improves cognitive functioning in individuals with mild-to-moderate AD.	measured by: The Mini-Mental State Examination(MMSE)
Exploratory Objectives	Exploratory Endpoints
To assess the effect of sargramostim treatment, as compared to placebo, on clinical progression in individuals with mild-to-moderate AD.	 Change in cognition from Baseline to EOT visit as measured by: the change in the MoCA (Montreal Cognitive Assessment) score the change in the ADAS-cog₁₃ (Alzheimer's Disease Assessment Scale-cognitive subscale) score the change in the Clinical Dementia Rating Scale Sum of Boxes (CDR-SB) score the change in the Trail Making Test A (TMT A) score the change in the ADCS-ADL (Alzheimer's Disease Cooperative Study Activities of Daily Living Inventory) score the change in the Neuropsychiatric Inventory Score (NPI) the change in tests of Verbal Fluency (Semantic and Lexical) scores
To assess the effect of sargramostim treatment, as compared to placebo, on metabolic activity in different brain regions in individuals with mild-to-moderate AD.	Change from Baseline to EOT visit in FDG-PET assessment of metabolic activity, overall, as well in different brain regions, particularly in the medial temporal lobe in potential correlation with changes in MTA

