7.4 Dosage Modification

Note: As the safety of the participant is paramount, the participants and their study partners will be told at the time of the informed consent that the study team will be monitoring their health and well-being through review of adverse events, laboratory results, and examinations performed during the trial. To help minimize the possibility of any unblinding of participants or study partners within any of these scenarios listed below, all participants will be informed at their time of consent that they may be asked to do one of three things if they are having adverse effects or abnormal laboratory results including: stopping treatment; receiving new, replacement syringes; or continuing treatment with the same syringes. Additionally, they will be told that the study team will continuously monitor their lab results, but they may not be told their specific results. Additionally, they will be informed that the trial physician or clinician designee will take the opportunity to examine them for clinical condition as a general safety measure if they are ever instructed to return to the CU-AMC site for an unscheduled visit.

The greatest safety concern noted with the investigational product is excessive leukocytosis. As advised by the product safety instructions, a CBC with differential, including examination for the presence of blast cells, will be competed twice weekly during the 24-week-long treatment phase. Additionally the product insert states that "If the ANC exceeds 20,000 cells/mm³ or if the platelet count exceeds 500,000/mm³, LEUKINE administration should be interrupted or the dose reduced by half. The decision to reduce the dose or interrupt treatment should be based on the clinical condition of the patient." If a participant has CBC with differential results which indicate that their ANC has exceeded 20,000 cells/mm³, their white blood cell count has exceeded 50,000 cells/mm³, or their platelet count has exceeded 500,000/mm³, the participant and the study partner will be immediately contacted, asked whether the participant is experiencing any adverse health effects, AND instructed NOT to administer any additional study product

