8.4.5.2 Protection of Participants

Because of the extensive safety history of sargramostim in elderly patients, serious safety issues are not anticipated, however, vigilance in assessing safety is required. A review of published AEs for GM-CSF and the Leukine[®] Product Insert and the papers it references will be used to guide the safety monitoring protocol (attached as Appendix E). The greatest safety concern noted with sargramostim is excessive leukocytosis. Therefore, as advised by the product insert, a CBC with differential, including analysis for blast cells, will be conducted at two time-points every week during the 24- week-long treatment phase. Refer to section 7.4 for details on dosage modification guidelines. In addition, the DSMB (described below) will monitor laboratory results, the MRI studies, and the cognitive assessments for any indications of toxicity. Following are the abbreviated categories of the National Cancer Institute's (NCI) graded toxicity protocol used by Daud et al., (2008) for assessing safety of Leukine^{® 123}, although the latest version of the NCI-CTCAE (Version 5.00: November 27, 2017) will also be referenced for all AEs (attached as Appendix F):

Anemia
Lymphopenia
Pain
Fever
Flu-like symptoms
Arthralgia/myalgia
Injection-site reaction
Fatigue
Abdominal cramps
GERD/indigestion
Insomnia
Cough
Sweating

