Common but non-life threatening side effects include:

- Fatigue or asthenia
- Malaise
- Rash
- Itching (pruritus)
- Vomiting
- Diarrhea
- Abdominal pain
- Sore throat (pharyngitis)
- Chills
- Bone pains
- Joint pains
- Weight loss or gain
- Elevations in kidney or liver enzymes
- Fluid retention (peripheral edema)
- Injection site irritation
- Insomnia
- Headaches
- Transient Fevers

Less common but potentially serious side effects include:

- Bleeding into the eye
- Allergic reactions
- Excessive increase in white blood cell count
- Fluid retention in the lung lining (pleura) and in the heart lining (pericardium)
- Shortness of breath
- Occasional transient heart rhythm changes (supraventricular tachycardia)
- Sweating, tachycardia, claustrophobia, or anxiety induced by the MRI procedure

Potential side effects of unknown frequency:

- Leukopenia (low white blood cell count)
- Neutropenia (low neutrophil count)

Adverse event of special interest (AESI) include:

An AESI is an AE (serious or non-serious) of scientific and medical concern specific to the program, for

which ongoing monitoring and immediate notification to the DSMB is required. Such events may require further investigation in order to characterize and understand them. Adverse events of special interest may be added or removed during a study by protocol amendment.

- ADA
- Acute hypersensitivity/anaphylaxis
- Leukopenia (low white blood cell count)
- Neutropenia (low neutrophil count)

Report of Unexpected Problems to the DSMB: The study coordinator will notify the PI or qualified sub-Investigator of any unexpected problems. The PI will contact the chair of the **DSMB** when unexpected problems arise that require immediate action.

Criteria for Action:

Specific triggers that will dictate when a specified action (such as reporting or stopping) is required. Any SAE or unexpected problem that meets the COMIRB criteria of reporting will be reported per COMIRB guidelines. Any serious AEs meeting the FDA reporting criteria, the FDA will also be notified according to their reporting guidelines.

Stopping rules:

Study: If treatment related serious AEs (SAEs) of Grade 3 or 4 occur in 20% of participants following sargramostim administration, the study will be stopped (Appendix F).

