Reporting mechanisms: AE forms will be completed and submitted on-line using the COMIRB AE reporting system. The report will include a description of the event, judgment as to whether or not it was related to study medication, and the outcome of the AE. All non-serious AEs, and those that are not unexpected or that are normal to the study medication, will be reported to the DSMB at the time in which the rest of data from an aggregate block of participants is submitted, or if the DSMB requests the information for their analysis in another trial-related matter.

Responsibility for preparing and submitting reports: The study coordinator will prepare the AE report and the PI or qualified sub-Investigator will review/edit as appropriate and the PI, study coordinator or other designated staff will submit the AE.

Confidentiality Procedures:

The meetings of the DSMB will be closed to respect the privacy of the research participants. Data will be kept in case report binders in a locked office when not in use. Data entered into the computerized data registry will only be accessible to those members of the research team.

9 Statistical, Data, and Other Considerations

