Appendix I

The DSMB will be chartered previous to the initiation of enrollment activities of the clinical trial. The Colorado Clinical and Translational Sciences Institute (CCTSI) will set up and manage an independent DSMB for this study. No staff at CCTSI work as personnel on this study, but they will recruit qualified scientific and medical professionals from inside and outside of the University of Colorado scientific community to review the patient safety data generated by this study. The appropriate DSMB member oversight will be managed by the leader of the CCTSI DSMB. The DSMB will meet at a regularly scheduled interval (every six months) to review participant safety data.

Assurance from Conflicts of Interest (COI): If recruited from the at-large CU-AMC professional community, members of the DSMB will be employed within different departments on the CU Anschutz Medical Campus, and no members have any real or perceived conflicts. All other members will be recruited from outside the University of Colorado scientific community. In addition, DSMB members will provide annual CU-mandated disclosures of any perceived or real COIs, and will notify fellow members of the DSMB, the trial's PI and/or Sponsor of any potential COIs that may arise during the trial.

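### The list of adverse events needing immediate DSMB notice omits ARIA, so a non-serious ARIA reaches the DSMB only in the aggregate report unless the investigator escalates it

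*Protocol*

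**What the plan says.** Section 8.4.5.3 (Data Monitoring Plan) describes an AESI as an adverse event, serious or non-serious, for "which ongoing monitoring and immediate notification to the DSMB is required". Four are listed: anti-drug antibodies, "Acute hypersensitivity/anaphylaxis", leukopenia and neutropenia. The list is closed in practice, because "Adverse events of special interest may be added or removed during a study by protocol amendment".

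ARIA is not listed. Yet the primary endpoint in Section 4.5 says that "high-resolution MRI scans to identify amyloid-related imaging abnormalities (ARIAs) will be performed", and the primary analysis in Section 9.2.1 includes assessing the MRI scans for vasogenic edema and microhemorrhage. Section 8.4.5.2 gives the DSMB the task of monitoring the MRI studies, along with laboratory results and cognitive assessments, for signs of toxicity. It sets no timeframe.

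Under Reporting mechanisms in Section 8.4.5.3: "All non-serious AEs, and those that are not unexpected or that are normal to the study medication, will be reported to the DSMB" together with the rest of the data from an aggregate block of participants, or when the DSMB asks for them.

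**The concern.** The AESI rule is the only provision that sends a non-serious event to the DSMB at once without depending on someone's judgement. ARIA is the imaging harm that the scheduled scans at weeks 6, 12, 18 and end of treatment are meant to detect. An abnormality found on such a scan in a participant without symptoms can easily be non-serious. Leaving it off the list means that the board charged with watching the MRI studies may learn of a primary-endpoint harm late, while other participants are being enrolled and treated.

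A second inconsistency adds to this. The AESI definition covers non-serious events, but the aggregate sentence speaks of all non-serious events and makes no exception for AESIs. Read literally, the two rules already conflict for the four events that are listed.

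**Working it through.** The protocol gives no figure to reproduce. The check is to follow an ARIA through each reporting route.

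**Step 1: who receives the MRI read.** Under Section 8.3.2, a blinded radiologist examines each scan for ARIA and reports to the study coordinator and study physician. No DSMB step is named.

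**Step 2: serious or not.** Section 8.4.5.1 defines an SAE by outcome (death, hospitalization, threat to life, disability, birth defect) or as an important medical event that may need intervention to prevent such an outcome. An ARIA without symptoms and without need for intervention does not have to meet that definition. Section 4.2, however, describes the ARIAs of earlier immunotherapy trials as SAEs, and Section 4.4.2 counts the absence of ARIA within its statement that no drug-related SAEs occurred. So the protocol leaves the classification open, and the speed of reporting depends on it.

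**Step 3: route to the DSMB.**

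| Case | Route | Section |
|---|---|---|
| Serious ARIA | Within five business days | 8.4.5.3, timeframe for reporting |
| Non-serious ARIA, judged an unexpected problem requiring immediate action | Principal investigator contacts the DSMB chair | 8.4.5.3, unexpected problems |
| Any other non-serious ARIA | With the aggregate block, or on DSMB request | 8.4.5.3, reporting mechanisms |
| Non-serious event on the AESI list, for comparison | Immediate | 8.4.5.3, AESI |

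By contrast, uncontrolled hypertension lasting more than two weeks has its own DSMB notice in Section 8.4.5.3. ARIA has none.

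**Step 4: possible delay.** The protocol does not say when aggregate reports are sent. Assume that they follow the DSMB meetings, which Appendix I schedules every six months: 52 / 2 = 26 weeks. A finding just before a report waits almost no time, and one just after waits up to about 26 weeks. Treatment lasts 24 weeks, and 26 > 24, so under this assumption the affected participant could finish treatment before the DSMB sees the event.

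**Step 5: the same check for leukocytosis.** Sections 7.4 and 8.4.5.2 both call it the chief concern ("The greatest safety concern noted with the investigational product is excessive leukocytosis"), and it is not an AESI either. Here the route is written down. Section 7.5 sends interruptions caused by an adverse event, including abnormal blood counts, to the regular aggregate reports. The reporting timeframe in Section 8.4.5.3 repeats this for Grade 2 blood-count results that require interruption. Section 7.4 adds blood counts twice a week and an automatic hold at set limits.

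**The case against.** The strongest reply is that ARIA may never take the slow route. The background sections group it with SAEs, and the SAE definition includes important medical events. The earlier trial saw none, so a first case could well count as unexpected. An independent medical monitor also evaluates adverse events and reviews safety reports quarterly or more often (Section 8.4.5). Further detail is left to a DSMB charter that is not at hand.

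Part of this stands. Serious cases do reach the DSMB within five business days, and escalation is possible. But Section 4.2 is background text, and neither Section 8.4.5.1 nor the AESI list names ARIA. Escalation rests on the principal investigator's judgement, and the medical monitor advises the sponsor and study team, not the DSMB.

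A reader might also infer three stronger things that the protocol does not support:

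- **Every ARIA and every leukocytosis case defaults to the aggregate report.** Serious cases do not. For leukocytosis the aggregate route is a deliberate choice, paired with the Section 7.4 algorithm, and not an accident of the list.
- **A participant with ARIA at week 6 stays exposed for the remaining 24 - 6 = 18 weeks until the DSMB acts.** The study physician receives each read, Section 7.5 allows interruption, and Section 8.4.5.3 allows discontinuation, all without the DSMB.
- **The delay could be 52 weeks.** The once-a-year meeting in Section 8.4.5.2 is a minimum. Appendix I sets the schedule at six months.

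**Conclusion.** The point holds for ARIA that does not meet the SAE definition. Such a finding, although part of the primary safety endpoint, has no assured prompt route to the DSMB. The delay could be up to about 26 weeks if aggregate reports follow the six-monthly meetings. It would be shorter if reports are sent between meetings, if the DSMB asks for the data, or if the investigator escalates.

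What is at stake is oversight across participants, since the study physician can act for the individual before the DSMB is told. The trial's results remain interpretable. This is a worthwhile and inexpensive correction, not a fundamental flaw.

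For leukocytosis no defect is shown. The only open question is whether the sponsor intends aggregate reporting for what Section 8.4.5.2 also puts first ("The greatest safety concern noted with sargramostim is excessive leukocytosis").

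**What to change.** 1. Add ARIA-E and ARIA-H to the AESI list in Section 8.4.5.3. State whether the entry means new findings relative to the screening MRI, because Section 6.1.2 excludes only participants with more than four microhemorrhages.
2. In Reporting mechanisms, state that AESIs are exempt from the sentence sending non-serious events with the aggregate block. This also removes the existing conflict for the four listed events.
3. Reconcile Section 4.2, which describes ARIAs as SAEs, with the definition in Section 8.4.5.1.
4. Confirm that aggregate reporting of leukocytosis under Sections 7.5 and 8.4.5.3 is intended. If the sponsor prefers to list it as an AESI, both of those provisions must change too, or a new contradiction arises. The number of extra notices could not then be taken as small: the remark in Section 7.4 about what is rarely expected concerns halving the dose, not the frequency of blood-count excursions.

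Items 1 to 3 need a protocol amendment and change no dose, threshold or treatment rule. The cost is a few more DSMB notices. Their number cannot be estimated from the earlier trial, which reported no ARIA but treated for 15 days over a 19-day period, not 24 weeks.

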- To assess the effect of sargramostim treatment, as compared to placebo, on changes in sleep-related measures in individuals with mild-tomoderate AD.
- To assess the effect of sargramostim treatment, as compared to placebo, on changes in speech measures in individuals with mild-to-moderate AD.

Study Design:

The study is double-blind, placebo-controlled in the Alzheimer's Disease population, and will include individuals with mild AD and moderate AD, consistent with Montreal Cognitive Assessment (MoCA) score range of 4-24 at time of screening. Individuals who meet inclusion/exclusion criteria will be randomized in a double-blind manner, to receive either sargramostim (178.57 $\mu g/m^2/day$ subcutaneously 7days per week for 24 weeks) or placebo (7 days per week) in an approximate 2:1 randomization ratio.

The study population will be recruited from the Memory Disorders Clinic at the University of Colorado Hospital (UCH) as well as from the community at large.

The estimated maximum duration of participation for each individual participant is approximately 10.5 months (12 week screening phase, 24 week post-randomization double blind treatment phase, and ~6 week (45 day) post-treatment follow-up phase.

Number of Study Participants

Approximately 150 individuals and their study partners will be screened, ~47 participants randomized, with an estimated 42 individuals completing the treatment and follow-up for full analysis (~28 individuals to the sargramostim 178.57 $\mu g/m^2/day$ subcutaneously arm of the study (1250 $\mu g/m^2$ per week) and ~ 14 individuals to the placebo control arm of the study.)

Protocol Synopsis (Continued)

Key Inclusion Criteria	Individuals between age 60 and 85 years, inclusive, at time of consent who meet criteria for probable AD dementia according to the National Institute of Aging – Alzheimer's Association (NIA-AA) research framework criteria (2018), and have a diagnosis of mild or moderate AD, or a study MD provisional diagnosis consistent with mild-to-moderate AD, with a screening MoCA score between 4-24, inclusive, have (optional per PI judgment of necessity) positive plasma biomarker for Alzheimer's disease, and have positive biomarker for brain amyloid pathology by CSF assay, obtained via screening lumbar puncture, or a positive amyloid PET scan.

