8.4.5.1 Serious Adverse Events

A serious adverse event, in relation to this clinical trial, is defined as something that results in:

- death.
- initial or prolonged inpatient hospitalization.
- a life-threatening event.
- persistent or significant disability.
- congenital birth defect.
- important medical events that might not be immediately life-threatening, or result in hospitalization, or death, but may require intervention to prevent such, including serious allergic reaction.

All AEs since the signing of the informed consent are to be assessed for seriousness, documented, and, if a serious adverse event, reported to the Sponsor within 24 hours of becoming known to the principal

investigator or qualified sub-Investigator. As well, the Data Safety Monitoring Board will monitor reported AEs and SAEs as a part of their role overseeing the protection of human participants.

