Full description of the DSMB will be provided in the charter. The DSMB will be comprised of members of relevant disciplines to overseeing conduct of a clinical trial for AD. The DSMB will be charged with overseeing participant safety. An initial meeting of the DSMB will be held before enrollment occurs in order for the members to review the study protocol and the study/participant termination guidelines. The DSMB will be required to meet at a minimum of one time per year. Data will be reviewed according to the DSMB mandated timeframe if a treatment related serious AE (SAE) or serious unexpected AE (SUAE) is reported. As mentioned above, SAEs and SUAEs will be reported per DSMB timeframes to the DSMB to discuss the SAEs/SUAEs and to decide whether the study should continue. Of note, if SAEs of Grade 3 or 4 occur in 20% of the initial 14 participants following sargramostim (or placebo) administration, the study will be halted while the Sponsor consults with the DSMB for final determination of study status. On the other hand, if the trial data indeed demonstrate clear safety and positive efficacy results from administration of sargramostim into AD participants at the end of the trial analyses, the DSMB may ethically consider and provide recommendations for open label extension study for trial participants, in which case the Sponsor will seek guidance from COMIRB and the FDA regarding how to proceed with these recommendations. All DSMB meetings will be documented and submitted to SARC. Once chartered, the DSMB membership will be listed in Appendix I.

8.4.5.3 Data Monitoring Plan: Data Recording:

These functions will be carried out by the study staff and transcribed into the case report forms (adverse events page). The principal investigator or qualified medical designee will review, edit, and sign off on the AE form, and the AE form filed by the PI or designated staff. Laboratory results and data from case report forms will be entered into a computerized data registry.

Data Verification: The PI or designated qualified sub-Investigator will discuss the AEs with the study coordinator(s), and will verify AE data entry.

Data to be monitored, assessed, and reported to/by the DSMB: (From Product insert)

Below is a list of possible data to be monitored, assessed and potentially reported to the DSMB. This list is not exhaustive, but comprised of information found in other studies of the investigational product.

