9.1 Sample size considerations

As the primary goal of this clinical trial is the safety and tolerability of long-term use of sargramostim in participants with mild-to-moderate Alzheimer's disease, a sample size of 42 participants (28 sargramostim-treated [1250 mcg/m²/ week subcutaneously], and 14 placebo equivalent) is considered sufficient to meet the endpoint of safety and is consistent with the lack of drug related SAEs in our recently-completed randomized, double blind, placebo-controlled trial of sargramostim in 40 (20 sargramostim-treated:20 placebo-treated) subjects with mild-to-moderate Alzheimer's disease.

Based on results for 40 participants at the EOT, 45-day follow-up, and 90-day follow-up in our recently completed sargramostim trial in participants with mild-to-moderate Alzheimer's disease, an effect size of

Mean Treatment Difference in Change from	Total	Number of	Number of		
Baseline to End of Treatment (Day 18)	Number of Patients	Sargramostim Patients	Placebo Patients	Alpha	Power
2	102	68	34	0.05	0.91
4	27	18	9	0.05	0.92
6	12	8	4	0.05	0.92
8	9	6	3	0.05	0.97

Table 1. Model for MMSE Total Score, Assumes no Treatment Effect at Baseline (successful randomization).

around 2–4 was predicted by the MMSE. We believe that the 42 participants (28 sargramostim-treated [1250 μ g/m²/week (178.57 μ g/m²/day subcutaneously seven days a week], and 14 placebo equivalent) who will be recruited for this study will provide sufficient power to allow valid analyses of the secondary and exploratory endpoints. Therefore, at least 42 individuals with mild-to-moderate Alzheimer's disease, age 60–85, of either sex, will be randomized (28 sargramostim participants and 14 placebo participants) for this proposed placebo-controlled study. For effect sizes of 2, 4, 6, or 8 (the expected treatment group differences in change between baseline and follow-up for MMSE total score), **Table 1** shows the number of participants required to achieve 91–97% power. Recruitment and treatment initiation will be timed to allow for the interim assessments before further participants are treated, thus assuring maximum early knowledge of any safety concerns.

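### Both study-level safety triggers count only Grade 3 or 4 SAEs, so read literally they leave out fatal ones

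*Protocol*

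**What the plan says.** The protocol has two study-level rules that tie a fixed percentage to a required action.

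- **Halt rule, Section 8.4.5.2:** "if SAEs of Grade 3 or 4 occur in 20% of the initial 14 participants following sargramostim (or placebo) administration, the study will be halted". The halt is a pause pending consultation between sponsor and DSMB. It covers either arm and does not require relatedness.
- **Stopping rule, Section 8.4.5.3 (Stopping rules):** "If treatment related serious AEs (SAEs) of Grade 3 or 4 occur in 20% of participants following sargramostim administration, the study will be stopped". It covers treatment-related SAEs after sargramostim and refers to Appendix F, which is CTCAE v5.0.

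Three other places bear on how these rules read.

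- **SAE definition, Section 8.4.5.1:** the list introduced by "A serious adverse event, in relation to this clinical trial, is defined as something that results in" starts with death and gives a life-threatening event as a separate item.
- **Grading scale, Section 8.4.5.2:** "the latest version of the NCI-CTCAE (Version 5.00: November 27, 2017) will also be referenced for all AEs". Section 9.2.1 uses the same scale for the primary safety analysis.
- **DSMB review, Section 8.4.5.2:** SAEs go to the DSMB "to discuss the SAEs/SUAEs and to decide whether the study should continue", with no grade limit.

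**The concern.** A range closed at Grade 4 excludes whatever the adopted scale places above it, and on CTCAE that is death. Neither rule adds an open upper end or mentions fatal events, and no other numerical rule in the protocol counts deaths. Taken literally, a Grade 3 SAE moves the study towards a mandatory halt, while a death in a participant with no earlier Grade 3–4 SAE does not.

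Safety and tolerability are the primary objective. Participants are aged 60 to 85. Section 5.1.2 records that the dosing schedule was changed because of possible unknown immune risks over six months, and Section 4.6.2 mentions infections that could be life-threatening. Section 8.4.5.3 introduces its criteria as triggers that determine when an action is required. A trigger of that kind should not rank the worst outcome below a Grade 3 event.

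**Working it through.** **Reading the text**

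1. Both rules use the closed form, Grade 3 or 4.
2. The protocol uses an open form elsewhere: Section 7.5 allows treatment interruption for AEs and laboratory values of Grade 2 or higher. So the closed form cannot be taken as the protocol's shorthand for an open one.
3. The participant-level rule in Section 8.4.5.3 also says grade 3 or 4. That does no harm there, because a participant who has died cannot be discontinued. In a study-level count it removes deaths.
4. The stopping rule cites the CTCAE appendix itself, so the grades are to be read on that scale. The protocol gives only the title and a link for Appendix F and does not print the grade definitions. That death lies above Grade 4 comes from the scale the protocol adopts, and it fits the separate listing of death and a life-threatening event in Section 8.4.5.1.

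**Effect on the counts**

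The rules give a percentage, read here as at least 20%. The number needed is 0.20 × n, rounded up to a whole participant.

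The inputs are:
- 14 initial participants, from the halt rule;
- 28 participants on sargramostim, from Section 9.1;
- about 31 dosed with sargramostim if the synopsis figure is used ("47 participants randomized, with an estimated 42 individuals completing the treatment and follow-up for full analysis") at 2:1 allocation: 47 × 2/3 = 31.3.

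| Rule and denominator | 0.20 × n | Needed | One death not counted | Same death counted |
|---|---|---|---|---|
| Halt rule, n = 14 | 2.8 | 3 | 2/14 = 14.3%, not met | 3/14 = 21.4%, met |
| Stopping rule, n = 28 | 5.6 | 6 | 5/28 = 17.9%, not met | 6/28 = 21.4%, met |
| Stopping rule, n = 31 | 6.2 | 7 | 6/31 = 19.4%, not met | 7/31 = 22.6%, met |

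Each row assumes that one participant's only qualifying SAE is the fatal one, and that all the others counted had a Grade 3–4 SAE. For the stopping rule all events must also be treatment-related. At the literal extreme, three such deaths among the first 14, or six related deaths among 28 on sargramostim, would count as zero.

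The protocol states no operating characteristics for these rules, so there is no figure of its own to reproduce. It gives no expected death rate either, so no probability is attached to these scenarios.

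**The case against.** The strongest reply is that deaths already have a faster and more sensitive route. A death is an SAE and goes to the sponsor within 24 hours. Trial-related SAEs go to the DSMB within five business days, and the DSMB decides on continuation without any minimum count. One related death can therefore open a stopping decision, while the numerical rules wait for three of 14 or six of 28. The halt rule itself only pauses the study until the DSMB is consulted. This is correct, and it limits the gap to the numerical backstop. It does not close the gap, because DSMB review is case-by-case judgement and the rules exist to require an action regardless of it.

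A second reply is that the premise lies outside the printed text: no grade is defined in the protocol, and Section 8.4.5.1 lists types of seriousness, not an ordered scale. It is fair that the definitions are not printed, and this lowers confidence somewhat. But the scale is one the protocol incorporates and the stopping rule cites.

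A third is that the DSMB charter and termination guidelines, which are not at hand, may deal with deaths. They may, but an unseen document cannot be assumed to correct a rule the protocol states in full.

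Finally, the affected case is narrow, since a participant with an earlier Grade 3–4 SAE already counts, and nobody is likely to regard a death as milder than a Grade 3 event. That supports calling this a drafting slip. It also concedes that the written rule does not say what is meant.

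**Conclusion.** The concern holds. As written, both study-level triggers omit a participant whose only qualifying SAE is fatal, and one such omission is enough to change the result: 2/14 against 3/14 for the halt rule, and 5/28 against 6/28 (or 6/31 against 7/31) for the stopping rule. This rests on the CTCAE v5.0 scale placing death above Grade 4, on reading the rules as at least 20%, and on the denominators in Section 9.1 and the synopsis. It does not mean that deaths go unreviewed, and no estimate or test is affected. With DSMB review in place the flaw is not critical. It should still be corrected, because a mandatory safety rule gives the wrong answer when followed literally.

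**What to change.** In the halt rule (Section 8.4.5.2) and the study stopping rule (Section 8.4.5.3), replace the Grade 3 or 4 wording with Grade 3 or higher, including fatal events. Check the DSMB charter and use the same wording there. Leave the 20% thresholds, the populations, the relatedness terms and the required actions unchanged. The participant-level rule needs no change.

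The cost is one phrase in two places and a matching line in the charter. The numbers needed stay at three of 14 and six of 28 (or seven of 31). The triggers become slightly easier to meet, because fatal events now count towards them.
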